# 2 METHODS: PARTICIPANTS, INTERVENTIONS, DEFINITIONS AND OUTCOMES

## 2.1 Study setting

This study will be multi-centre and will take place in at least three hospitals, to increase the generalisability of the results. Any hospital in England that employs nurses who meet the participant inclusion and exclusion criteria (Section 2.2) will be eligible to be a study site. All sites will carry out the same activities, namely recruiting participants and hosting the *in situ* simulation.

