## 2.5 Outcomes

#### 2.5.1 Primary outcome

The primary outcome will be the observed rate of IMG-related moderate-severe errors in each group. Following the approach of recent meta-analyses, error rates will be expressed as percentages using the number of doses considered to have one or more errors as the numerator and the total number of doses as the denominator.

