#### 2.7 Sample size

There is one published study that reports the rate of moderate to severe errors in the preparation and administration of intravenous medicines to adults on UK hospital wards and which used the same error observation and severity determination techniques as this study. This study observed one or more moderate-severe errors in 30% of 430 intravenous doses. If the definitions to be used for the current study had been applied in this previous research, 27.2% of 430 intravenous doses would have involved one or more moderate-severe IMG-related errors.

Using the same techniques, a larger and more recent, but as yet unpublished study, observed one or more moderate-severe preparation errors in 28% of 1148 adult injectable medicine doses administered on UK hospital wards. This study did not investigate administration errors, but their inclusion would have increased this error rate.

These error rates are supported by other studies, which either took place in other countries or used different severity determination methods, which report similar rates of moderate-severe preparation and administration errors (22-34% of doses).

Therefore, it is reasonable to assume that participants in the "original monograph" group will make at least one moderate-severe IMG-related error in 30% of doses.

Following discussion with the Study Advisory Group, it was agreed that at least one moderate-severe error occurring in 15% of doses would represent a clinically relevant reduction. This is in line with the assumptions underlying other recent research considering the effect of educational interventions on the rate of injectable medicine preparation and administration errors.

Standard calculations indicate that a sample size of 121 participants per group will give an 80% probability of detecting this reduction in the moderate-severe error rate at the 5% significance level, assuming equal group size. This assumes that there is no clustering of the data by hospital site, as NHS hospitals are required to provide similar training for staff preparing and administering intravenous medicines, and to follow similar procedures.

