# 3 METHODS: ASSIGNMENT OF INTERVENTIONS

## 3.1 Sequence generation

The allocation sequence will be generated using an online blocked randomisation list generator (www.sealedenvelope.com/simple-randomiser/v1/lists). A block size of 10 will be employed. Allocation will be stratified by research site and nursing experience, to ensure equal representation of nurses employed by different hospitals and with different levels of experience in each group.

Nursing experience will be measured by the total number of years each participant has been accredited for the administration of intravenous medicines, with two strata: <5 years and ≥5 years. A cut off of five years of experience preparing and administering intravenous medicines was chosen because evidence suggests that the number of errors with which a nurse is involved decreases over the first four to six years of their nursing experience. In particular, one study found that the risk of intravenous medicine administration errors decreased with each year of a nurse's experience up to six years.

The allocation sequence will link each participant's unique randomisation code to their allocation groups: A or B.

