#### Statistical analysis of observation data

Statistical analysis will be performed using SPSS, STATA, R and Microsoft Excel.

There are plausible reasons for each of the following participant characteristics modulating the effect size of both the primary and secondary outcomes:

- Participants whose first language is not English.
- Participants with <5 years' experience of administering intravenous medicines, because evidence suggests that the number of errors with which a nurse is involved decreases over the first four to six years of their nursing experience. In particular, one study found that the risk of intravenous medicine administration errors decreased with each year of a nurse's experience up to six years.
- Participants who have previously used the national IMG on a regular basis, as they will be familiar with the layout of the "original" monograph.

Therefore, these characteristics will be considered during the analysis.

First, the data derived from the severity scoring panel will be analysed. The mean severity score allocated by the panel for each confirmed error will be calculated. The potential severity of the outcome for each error will be determined from this mean severity score, as follows:

- Mean severity score <3 = minor outcome
- Mean severity score 3-7 = moderate outcome

• Mean severity score >7 = severe outcome

The inter-rater reliability of the severity scoring panel will be investigated by the calculation of Cronbach's alpha. A coefficient  $\geq$ 0.70 will be considered an indicator of acceptable reliability. The validity of the severity scoring panel will be investigated by comparing the mean severity scores of the actual errors with their known outcomes (minor, moderate or severe).

Subsequently, the moderate-severe IMG-related error rate (primary outcome), the minor IMG-related error rate, and the moderate-severe and minor non-IMG-related error rates will be calculated, based on the above analysis of the severity scores. Following the approach of recent meta-analyses, each error rate will be calculated as a percentage as follows:

 $Error rate = \frac{Number of observations containing one or more errors}{Total number of observations} \times 100$ 

Where one observation contains more than one error, it will be allocated the severity category of the most severe of the individual errors.

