Each of these four error rates will then be compared between the two groups using a Chi squared test at the 5% significance level (one test for each hospital site and one for the overall data). This will be followed by a mixed effects logistic regression analysis, with hospital site as the random effect and the other characteristics as fixed effects.

Subject to the distribution of the data, the mean and standard deviation of the time taken for each group to complete the *in situ* simulation will be calculated. These will be compared using time to event analysis (depending on the distribution of the data, probably a Cox proportional hazards model), considering the data from each hospital. The overall data will also be analysed in a similar fashion, with the model incorporating hospital site as a random effect and the other characteristics as fixed effects.

Participant responses to the mPDPAI questions will be used to calculated a modified Decision Conflict Score (mDCS), following the methods described for the original PDPAI. Participants responses to these questions will use a five point Likert scale ranging from strongly agree (scoring 1) to strongly disagree (scoring 5). To calculate a participant's mDCS, the Likert scores will be summed for questions 13 to 20 of the data collection tool, after reversing the scores for question 13, 14, 16 and 17. It will therefore be possible for the mDCS to range from 8 to 40, with a higher score reflecting a higher degree of uncertainty whilst preparing and administering bathicillin.

Individual participants' mDCS will be derived. Subject to the distribution of the data, linear regression will be used to analyse the effects of IMG monograph, hospital, first language, nursing experience and previous IMG experience on the mDCS score.

The psychometric properties of the mPDPAI in the study population will be investigated using the methods used in the initial development of the PDPAI. Item homogeneity will be evaluated by calculating Pearson correlation coefficients between each item and a revised mDCS calculated by removing that item from the total score. Outliers will be defined as items with a correlation coefficient less than 0.2. Inter-item reliability will be investigated by the calculation of Cronbach's alpha. A coefficient the range 0.70-0.90 will be considered an indicator of acceptable reliability.

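### The overall chi-squared test (implied primary) ignores the randomisation strata; per-hospital 5% tests stand unranked beside it; stated effect modifiers enter only as main effects

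*Protocol*

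**What the plan says.** - **Tests.** Protocol section 4.3 (Statistical analysis of observation data) compares four error rates, one of them the primary outcome, between the groups "using a Chi squared test at the 5% significance level (one test for each hospital site and one for the overall data".
- **Model.** A mixed logistic regression follows, "with hospital site as the random effect and the other characteristics as fixed effects". The section neither ranks these analyses nor says what happens if they disagree.
- **Characteristics.** The same section gives reasons for first language, experience under five years and regular earlier use of the guide "modulating the effect size of both the primary and secondary outcomes". It says only that they will be considered. No product term with monograph is mentioned.
- **Randomisation.** Section 3.1: "Allocation will be stratified by research site and nursing experience", with experience split at five years.
- **Sites.** Section 2.1: the study "will take place in at least three hospitals". Section 2.7 expects four.
- **Primary outcome.** Section 2.5.1: "The primary outcome will be the observed rate of IMG-related moderate-severe errors in each group".

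**The concern.** Three features of the analysis do not match the rest of the design.

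1. Stratified allocation makes the arms more alike than simple randomisation would. An overall test that leaves the strata out does not use that balance, so its standard error is too large when the strata predict errors. The protocol itself cites evidence that experience does.
2. Several 5% tests address the one primary question and none is labelled as deciding it. A report could stress whichever hospital gave a small p-value. A mix of significant and non-significant hospitals could also be taken as evidence that the monograph works in some places and not in others.
3. A main effect describes how a characteristic shifts the error rate in both arms alike. Whether it changes the monograph's effect is a question of interaction, and the planned model has no term for that.

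**Working it through.** **Inputs.** Control rate 30% (section 2.7: "will make at least one moderate-severe IMG-related error in 30% of doses"); target rate 15% ("at least one moderate-severe error occurring in 15% of doses would represent a clinically relevant reduction"); 1:1 allocation; 5% level, taken as two-sided; 80% power; 121 to 172 per group; three or four sites.

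**Step 1: the plan's own figure.** With mean rate 0.225,

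n = [1.96·√(2·0.225·0.775) + 0.8416·√(0.3·0.7 + 0.15·0.85)]² / 0.15² = (1.1575 + 0.4889)² / 0.0225 = 120.5, so 121 per group.

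This reproduces the protocol. It is an unadjusted two-proportion calculation on the whole sample, so among the listed analyses it matches the overall chi-squared test.

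**Step 2: power of one hospital's test.** Power = Φ[(0.15·√m − 1.1575) / 0.5810], where m is the number per group in that hospital, assuming equal sites.

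| Per group, total | Sites | m | Power |
|---|---|---|---|
| 121 | 3 | 40.3 | 36% |
| 121 | 4 | 30.25 | 28% |
| 172 | 3 | 57.3 | 49% |
| 172 | 4 | 43 | 38% |

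With four sites, 121 per group and the same true effect everywhere, the chance that some site tests are significant and others not is 1 − 0.2836⁴ − 0.7164⁴ = 1 − 0.006 − 0.263 = 73%. A mixed pattern is thus the expected result under complete homogeneity.

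**Step 3: false positives if any test counted.** The site tests alone give 1 − 0.95³ = 14.3% or 1 − 0.95⁴ = 18.5%. Adding the overall test, a 20,000-run simulation at 120 per group with no stratum effects gives 15.9% (three sites) and 20.0% (four sites).

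**Step 4: cost of leaving out the strata.** The same simulation compared the overall chi-squared test with a Cochran-Mantel-Haenszel (CMH) test over hospital × experience, at 30% v 15% and 120 per group with equal strata. Only the intraclass correlation (ICC) of 0.01 comes from the protocol. The larger ICCs (all applied on the logit scale) and the experience odds ratios (OR) are assumptions.

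| Strata | Sites | Type I: overall / CMH | Power: overall / CMH |
|---|---|---|---|
| ICC 0.01, OR 2 | 3 | 4.8% / 5.1% | 79.4% / 80.0% |
| ICC 0.01, OR 2 | 4 | 4.4% / 4.8% | 80.3% / 80.8% |
| ICC 0.05, OR 2 | 3 | 4.5% / 4.9% | 78.9% / 79.7% |
| ICC 0.05, OR 2 | 4 | 4.6% / 5.1% | 78.9% / 80.0% |
| ICC 0.2, OR 3 | 3 | 3.2% / 4.8% | 73.1% / 77.0% |
| ICC 0.2, OR 3 | 4 | 3.4% / 5.2% | 72.6% / 77.1% |

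The loss is about 0.5 to 1 point with modest strata and about 4 points with strong ones. In every row the error is on the conservative side.

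**Step 5: what an interaction test could show.** Take an extreme case, which is an assumption: the rate falls from 30% to 15% in one half of participants and does not change in the other half. At 121 per group each cell holds 60.5 nurses. The difference in log odds ratios is 0.887 and its variance is 1/(60.5·0.1275) + 3/(60.5·0.21) = 0.366. Power = Φ(0.887/0.605 − 1.96) = 31%. At 172 per group it is 42%. Such a test can only be exploratory, but it asks the question the protocol raises.

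**The case against.** The best defence is that the protocol leaves little real doubt about the main comparison. Section 1.4 sets one guide against the other, section 1.5 frames superiority between them, the primary outcome is a rate in each group, and the sample size is an overall two-group calculation. The regression comes after the tests, and section 2.7 links the study of site and other variables to the optional larger sample. Site tests with 28% power were plainly not designed to decide anything. All of this stands, and it is why the overall test is treated here as the implied primary.

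The strata are also not absent from the plan. Each hospital's test holds site fixed, and the mixed model carries both site and experience. Only the overall chi-squared test uses neither. At the protocol's own ICC the cost is half a point of power. This also stands.

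A reader might infer that a random effect on three or four hospitals spoils the model. Its variance is indeed poorly estimated. But nurses are randomised individually within site, and a zero estimate simply gives ordinary logistic regression. A 6,000-run simulation of that case (four sites, 240 nurses, ICC 0.01, experience OR 2) gave type I error 4.8% and power 79.7%, against 5.1% and 80.2% with site fixed. The harm is negligible.

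On effect modification, the defence is that it is not an objective, that the experience argument reads mostly as prognostic, and that exact interaction terms can be left to a statistical analysis plan, which was not available here. This stands only in part. The protocol states a purpose and then fixes a model that cannot serve it. The argument about earlier use of the guide is clearly an interaction argument, since knowing the original layout would help mainly in the original-monograph arm.

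**Conclusion.** The point holds as a should-fix. The overall test is valid but slightly inefficient, by the margins in step 4. The larger loss depends on stratum effects well beyond the ICC the protocol assumes. The per-hospital tests are weak, are not declared non-deciding, and cannot show whether the effect differs between sites. The three characteristics are given an effect-modification rationale that main effects cannot address.

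Two stronger readings are tempting and not supported. One is that the trial runs at a false-positive rate near 20%. That figure requires a single hospital's p-value to count as success, and nothing in the protocol says it does. The other is that ignoring the strata inflates type I error. It lowers it.

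The figures assume equal sites, equal stratum sizes and error rates of 30% and 15%.

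**What to change.** In section 4.3:

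- Name one primary analysis: the overall comparison stratified by hospital and experience (under five years, five years or more). A Cochran-Mantel-Haenszel test with a stratified risk difference and 95% confidence interval would serve, as would a logistic model containing those terms.
- Replace the per-hospital p-values with site-specific estimates and confidence intervals, plus one arm-by-site interaction.
- Add interactions of monograph with first language, experience and earlier use of the guide, labelled exploratory.
- Optionally, enter hospital as a fixed rather than random effect. With three or four sites this is simpler and changes the treatment estimate little.

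The cost is some rewording and a little more analysis code. The plan already uses all of these variables, and the stratified test needs no larger sample. The interactions will be imprecise and should be reported as such.

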#### 2.5.2 Secondary outcomes

There will be a number of secondary outcomes:

[figure not shown]
- The rate of IMG-related errors of any severity in each group
- The rate of moderate-severe non-IMG-related errors. This outcome will be measured because it is hypothesised that a more easily understood IMG monograph will enable participants to concentrate more on other aspects of the injection preparation and administration process.
- The rate of non-IMG-related errors of any severity in each group
- The mean time taken to prepare and administer the dose for each group. For each participant, the time will be measured from the point at which they start to read the simulated medication order or IMG monograph until the point at which they inform the observer that they would leave the simulated patient's bedside with the infusion running. This outcome will be measured

because it is hypothesised that a more easily understood IMG monograph will be read and interpreted more quickly, thus reducing the time required to prepare and administer the dose.

- The mean modified Decision Conflict Score (mDCS) for each group. This will be calculated from participant's responses to a modified Provider Decision Process Assessment Instrument (mPDPAI) immediately after they have finished preparing and administering the intravenous infusion. The mDCS is a measure of participants' degree of knowledge and uncertainty whilst making decisions during the preparation and administration of the medicine. It will be measured because it is hypothesised that a more easily understood IMG will result in participants having great confidence in the decisions made during the dose preparation and administration process.
- The mean monograph preference score of each group. Immediately after completing the mPDPAI, each participant will be shown the version of the IMG monograph they did not use to prepare the dose of medicine and asked to rate their preferred version using a seven point Likert scale. This will be measured because it is hypothesised that participants will prefer the more easily used IMG.

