## Missing data

As all data will be collected in a single session, techniques to promote participant retention are not necessary and it is likely that complete data will be obtained from all participants. However, should a participant choose to leave the study before completing *in situ* simulation, their data will be discounted. If a participant completes the *in situ* simulation but does not complete the subsequent secondary outcome measures, the observational data collecting will be included in the final data set, along with their mPDPAI and preference data, if complete.

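### The time outcome is defined as a mean per group, but the comparison proposed is a time-to-event analysis, probably Cox, which does not compare means

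*Protocol*

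**What the plan says.** Section 2.5.2 lists as a secondary outcome "The mean time taken to prepare and administer the dose for each group". The reason given is that "a more easily understood IMG monograph will be read and interpreted more quickly, thus reducing the time required to prepare and administer the dose".

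Section 4.3 (Statistical analysis of observation data) plans, subject to distribution, to calculate "the mean and standard deviation of the time taken for each group". It continues: "These will be compared using time to event analysis (depending on the distribution of the data, probably a Cox proportional hazards model". This is done by hospital, and then: "The overall data will also be analysed in a similar fashion, with the model incorporating hospital site as a random effect", with the listed participant characteristics as fixed effects.

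The missing-data paragraph of section 4.1 says of anyone who leaves before finishing the simulation that "their data will be discounted".

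The protocol gives no expected mean, standard deviation, effect size or power for time.

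**The concern.** The quantity named as the outcome and the quantity the proposed model estimates are different. Group means are to be calculated, and the next sentence compares them with a class of model whose named member does not compare means. A Cox model asks whether the instantaneous rate of finishing, among those still working, is the same in both groups at every moment.

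Time-to-event methods are normally chosen because some times are censored. Here every analysed participant has a fully observed time, so that reason is absent and the protocol offers no other. Two other scores are treated more directly in section 4.3: the decision conflict score gets linear regression, and the preference score gets a difference in means with a confidence interval.

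At stake is whether the trial can say how many minutes the revised monograph saves, with an interval, and whether a significant result on time means that mean time differs.

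**Working it through.** **Group sizes.** The protocol has no figure for time to reproduce, so only the group sizes are taken from it. The minimum of 121 per group (section 2.7, 30% v 15%, two-sided 5%, 80% power) reproduces:

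n = [1.96·√(2·0.225·0.775) + 0.8416·√(0.30·0.70 + 0.15·0.85)]² / 0.15² = (1.157 + 0.489)² / 0.0225 ≈ 120.5, so 121.

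The upper size is 172 per group (section 2.7).

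**Assumptions, because the protocol has no timing data.** Control mean of 20 minutes; no censoring; no covariates and no site effect; several distribution shapes and spreads.

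**Tests compared, both two-sided at 5%.**
- Cox score (log-rank) test without ties: Z = Σ(d₁ⱼ − n₁ⱼ/nⱼ) / √Σ(n₁ⱼn₂ⱼ/nⱼ²). The sum runs over finishing times, with n₁ⱼ, n₂ⱼ still working in each group, nⱼ = n₁ⱼ + n₂ⱼ, and d₁ⱼ = 1 if the finisher is in group 1.
- Welch comparison of means: T = (x̄₁ − x̄₂) / √(s₁²/n + s₂²/n).

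**Step 1: equal means, log-normal times.** Proportion of simulated trials rejecting:

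| log-SD in the two groups | Cox, 121 per group | Cox, 172 per group | Welch |
|---|---|---|---|
| 0.30 / 0.30 | about 5% | about 5% | about 5% |
| 0.30 / 0.35 | about 6% | about 6–7% | about 5% |
| 0.30 / 0.40 | about 8% | about 10% | about 5% |
| 0.25 / 0.40 | about 14% | about 18% | about 5% |

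Other shapes widen the range. With coefficients of variation 0.30 v 0.40, Cox rejected in 8–23% of trials at 121 per group across log-normal, gamma, Weibull and normal times. With 0.20 v 0.40 it was 25–74%.

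**Step 2: a constant saving in minutes.** The saving is sized to give the comparison of means 80% power: d = (1.96 + 0.8416)·SD·√(2/n).
- n = 121, SD 5 (20 × 0.25): d = 2.8016 × 5 × 0.1286 ≈ 1.8 minutes.
- n = 121, SD 8 (20 × 0.40): d = 2.8016 × 8 × 0.1286 ≈ 2.9 minutes.

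Welch then has about 80% power. Cox has 64–65% for log-normal and gamma times, 71% for normal and 67–77% for Weibull. Results at 172 per group are nearly the same.

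**Step 3: a proportional saving in total time, 121 per group.** Cox v Welch: log-normal 77–81% v 84–85%; gamma 79–83% v 83–85%; Weibull, where proportional hazards hold exactly, 89–91% v 83–85%.

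**Step 4: only the reading part shortened by a factor, 121 per group.** Cox 72–93% v Welch 81–87%. Cox is lower in 7 of 12 scenarios and about equal or higher in 5.

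Steps 2 to 4 show that the direction of the power difference depends on how the saving is distributed across nurses.

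**The case against.** Several stronger readings are tempting, and the protocol does not support them.

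- **That Cox is fixed.** It is not. Section 4.3 calls it probable and conditional on the distribution. Every option named is a time-to-event analysis, but that class includes accelerated failure time models, which compare times directly. The point is therefore against the model named as likely, and against leaving the effect measure unaligned with the outcome.
- **That the plan loses power for its own hypothesis.** Section 2.5.2 says only that reading and interpretation will be quicker. It does not state a constant saving on an otherwise unchanged task. Section 4.3 expects first language, experience and prior use of the guide to modify effects, and section 2.5.2 suggests that an easier monograph may change attention to the rest of the task. Under some such patterns Cox gains power.
- **That the false-positive rate is generally inflated.** Under identical distributions the Cox test holds 5%. Excess rejection requires equal means with a different spread or shape. Nothing in the protocol predicts that, and such a rejection would still reflect a real difference in the times, though not in the mean.
- **That the protocol states a null of equal means.** It states a mean per group and implies a comparison; it writes no null.

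It is also fair that the absence of censoring makes Cox unnecessary, not invalid; that group means and standard deviations are to be reported anyway, so a crude difference could be derived; and that final model choice may sit in a statistical analysis plan not seen here. What remains is that this document names an outcome and a likely method that do not match, and plans no adjusted difference in minutes.

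**Conclusion.** The mismatch between outcome and proposed model is in the text and should be corrected. Its consequences are conditional. With equal means and unequal spread, the Cox test rejects in about 8–14% of trials at 121 per group and 10–18% at 172, for log-SD 0.30 v 0.40 or 0.25 v 0.40. Its power is about 65% against 80% for a constant saving under log-normal times, and higher than that of the means comparison when a proportional saving meets proportional hazards. All these figures rest on an assumed 20-minute mean, assumed shapes and spreads, and no site effect or covariates. The certain consequence is narrower: the model named as probable gives a hazard ratio for finishing and no adjusted number of minutes saved. This is a secondary outcome; the primary analysis and its conclusion are unaffected.

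**What to change.** In section 4.3, state that the main result for the time outcome is the adjusted difference in mean minutes between monographs with its 95% confidence interval. Obtain it either from a linear model with heteroscedasticity-robust standard errors and site terms, or from a linear mixed model that keeps the planned random effect for hospital site. Either way, monograph, the experience stratum and the other listed characteristics enter as fixed effects.

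Keep a Cox or log-time model as supportive and label it so. A log-time model is not a substitute for the main result, because it compares means of log time: with equal means of 20 minutes and coefficients of variation 0.25 v 0.40 (log-normal, 172 per group), a t-test on log time rejected in 24% of simulated trials.

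The cost is a change of wording and one simple regression on data already planned, with no extra participants. The small downside is that an untransformed mean is more sensitive to a few very slow sessions; the supportive model would show whether they drive the result.

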Previously, construct validity was investigated by hypothesising that there would be a negative correlation between the DCS and participants' rating of the quality of the decision and their satisfaction with it. The same hypotheses will be investigated for the mDCS by calculating Spearman's correlation coefficients between participants' mDCS and their responses to the quality and satisfaction validation questions (questions 21 and 22 in data collection tool). For analysis, the rating scale responses to the satisfaction question question (question 22 in data collection tool) will be transformed into an ordinal scale ranging from 1 ("terrible") to 7 ("delighted"). Negative correlation between these variables will support the credibility of the two hypotheses outlined at the start of this paragraph and the validity of the mPDPAI.

Construct validity will be further investigated by testing two new hypotheses. The first new hypothesis is that that nurses who are more uncertain about how to prepare and administer the dose will take longer to complete this task. This will be investigated by calculating the Spearman's rank correlation coefficient between the mDCS scores and the time taken to complete the *in situ* simulation. Positive correlation between these variable will support the credibility of this first new hypothesis and the validity of the mPDPAI.

The second new hypothesis is that nurses who are more uncertain about how to prepare and administer the dose will be more likely to make one or more IMG-related errors (of any severity). This will be investigated by logistic regression between the mDCS score and the presence or absence of IMG-related errors for each participant. An odds ratio with a 95% confidence interval which does not cross 1.0 will support the credibility of this second new hypothesis and the validity of the mPDPAI.

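### Three of the four construct-validity rules for the modified decision questionnaire pass on the sign of a correlation alone; the fourth omits its direction, and none accounts for monograph group

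*Protocol*

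**What the plan says.** The rules stand in Protocol section 4.3, under Statistical analysis of observation data.

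- **Quality and satisfaction.** The method is "calculating Spearman's correlation coefficients between participants' mDCS and their responses to the quality and satisfaction validation questions". The criterion is "Negative correlation between these variables will support the credibility of the two hypotheses outlined at the start of this paragraph", and the same sentence extends the support to the validity of the instrument.
- **Time.** A Spearman correlation between mDCS and simulation time is calculated. The criterion is "Positive correlation between these variable will support the credibility of this first new hypothesis and the validity of the mPDPAI".
- **Errors.** The hypothesis reads: "nurses who are more uncertain about how to prepare and administer the dose will be more likely to make one or more IMG-related errors". The method is "logistic regression between the mDCS score and the presence or absence of IMG-related errors for each participant", and the criterion is "An odds ratio with a 95% confidence interval which does not cross 1.0 will support the credibility of this second new hypothesis".

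The mDCS runs from 8 to 40, "with a higher score reflecting a higher degree of uncertainty whilst preparing and administering bathicillin", so the error hypothesis corresponds to an odds ratio above 1 per mDCS point.

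Other parts of the Protocol bear on these rules. Section 4.3 gives numeric criteria for item-total correlations (0.2) and for Cronbach's alpha (0.70 to 0.90). Its regression for mDCS as an outcome includes the monograph as a term. Section 4.1 reports correlations of -0.58 and -0.52 for the original instrument. Section 2.5.2 expects the user-tested monograph to make nurses more confident and quicker.

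**The concern.** These sentences are decision rules stated in the Protocol: they say what result will be read as support. They are therefore not a detail left for a statistical analysis plan.

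For three of the four checks, a coefficient of -0.01 (or +0.01 for time) counts the same as -0.58. The rule cannot tell a valid instrument from noise. The odds-ratio rule does use an interval, but it does not restate the direction.

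The monograph is a common cause that the trial itself predicts. If it lowers mDCS and time together, or mDCS and errors together, the whole sample shows an association even when mDCS says nothing about which nurses within an arm are slower or make errors. Both new hypotheses are worded about individual nurses.

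What is at stake is the validity claim for an instrument that lost four of its twelve items and had the rest reworded, and hence the weight given to one secondary outcome.

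**Working it through.** **Inputs from the Protocol.** 121 participants per group, with 172 as the upper figure; planning rates of 30% v 15% for moderate-severe IMG-related errors (section 2.7); the four rules above.

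**Assumptions, because the Protocol gives no figures.** Monograph shifts of d = 0.2, 0.5 and 0.8 SD, taken as equal for mDCS and time; 30% v 15% used as the error rates in the logistic check, although that check concerns errors of any severity; no association between mDCS and the other variable within either arm.

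**Step 1: the plan's own figure.** With mean rate 0.225, n = [1.96 × √(2 × 0.225 × 0.775) + 0.842 × √(0.30 × 0.70 + 0.15 × 0.85)]² / 0.15² = 120.5, so 121 per group. This reproduces the stated figure and fixes N = 242. It is not in dispute.

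**Step 2: sign-only rule, no association.** The coefficient is symmetric about zero, so the right sign appears with probability 1/2. Simulation (4,000 trials) gives 50.6%.

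**Step 3: sign-only rule for time, shared monograph shift only.** With equal arms the whole-sample Pearson correlation is (d²/4) / (1 + d²/4). By Fisher's z, the chance of a positive sign is Φ(artanh(r) × √(N − 3)), with √239 = 15.46.

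| d | r | Φ(artanh(r) × 15.46) | Simulated Spearman, right sign | Simulated, right sign and p < 0.05 |
|---|---|---|---|---|
| 0.2 | 0.010 | 56% | 56% | 3% |
| 0.5 | 0.059 | 82% | 81% | 14% |
| 0.8 | 0.138 | 98% | 98% | 57% |

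At 172 per group the right-sign figures are 57%, 86% and 99.6%.

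**Step 4: odds-ratio rule, shared monograph effect only** (1,500 simulated trials, 121 per group, 30% v 15%).

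| d for mDCS | Unadjusted 95% interval wholly above 1 | Wholly below 1 |
|---|---|---|
| 0.2 | 4% | 0.7% |
| 0.5 | 10% | 0.4% |
| 0.8 | 18% | 0% |

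With a monograph term, the interval excludes 1 on either side in 4% to 5% of trials, so about 2% to 3% in the hypothesised direction. With no monograph effect at all, the unadjusted interval lies wholly below 1 in about 2% of trials.

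Other assumed error rates over the same shifts give 4% to 8% (60% v 50%) and 4% to 13% (90% v 80%) for an unadjusted interval above 1.

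**Step 5: what a proper criterion demands.** An interval that excludes zero at two-sided 5% needs |r| > 1.970 / √(240 + 1.970²) = 0.126 at N = 242. Power at a true |r| of 0.2 is Φ(artanh(0.2) × 15.46 − 1.96) = Φ(1.17), about 88%; at 0.3 it exceeds 99%. Correlations near those of the original instrument would pass almost surely.

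The last column of the Step 3 table shows that an interval criterion on the whole sample does not by itself remove a large shared shift. That is why a monograph-adjusted analysis is also useful.

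**The case against.** A reader might infer two stronger points that the Protocol does not support.

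**That a contrary result would be accepted as validation.** Read alone, the interval sentence would admit an odds ratio wholly below 1. But it refers back to a hypothesis in the same paragraph that is plainly directional, and a careful analyst would apply that direction. Even on the literal reading, a contrary interval arises in only about 2% of trials with no effect, and in less than 1% in the scenarios of Step 4. The correlation rules do not admit the wrong sign at all. This is a slip of wording.

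**That validity could be claimed from the monograph effect alone.** Several things limit this:

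- The Protocol never says that the arms are pooled. That is the plain reading, but it rests on silence, and a statistical analysis plan not available here could add the term.
- If mDCS moves with a predicted difference between arms, that is partly legitimate known-groups evidence. A whole-sample analysis is therefore not an error in itself.
- Section 2.5.2 predicts no monograph effect on the quality and satisfaction ratings, so the mechanism applies to time and errors only.
- The sizes depend on assumed inputs. A 0.2 SD shift leaves the time sign close to chance. A figure as high as 44% for the odds ratio needs a 0.8 SD shift with error rates of 80% v 50%, a difference twice the planning one.

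It is also fair that 50% is the pass rate of one correlation, not the chance of an overall validity claim. Item-total correlations and Cronbach's alpha are also examined, nothing is gated on the result, and a reported r of 0.06 to 0.14 would look weak beside -0.58 and -0.52.

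None of this rescues the sign-only rules.

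**Conclusion.** The point holds, and it is minor. The firm part is that the quality, satisfaction and time rules accept any coefficient of the right sign, so each passes about half the time with no association; this needs no assumed effect size. The odds-ratio rule should carry the direction that its hypothesis already states.

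The monograph part supports an added analysis rather than a charge of error. Under assumed shared shifts of 0.2 to 0.8 SD and no within-arm association, the time check passes in about 56% to 98% of trials at N = 242. At assumed error rates of 30% v 15%, the unadjusted odds ratio is significantly above 1 in roughly 4% to 18%, against 2% to 3% with group in the model. Those shifts and rates are assumptions; any-severity error rates may well differ from the moderate-severe planning rates.

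The primary outcome, the sample size and the between-arm comparison of mDCS, whose model already includes the monograph, are unaffected.

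**What to change.** Change the criteria in section 4.3 as follows.

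- Count a correlation as support only if its 95% interval excludes zero in the hypothesised direction (about |r| > 0.126 at N = 242), and report the coefficient with its interval.
- For the error check, require the lower 95% limit of the odds ratio per mDCS point to be above 1.0.
- Beside the whole-sample results, report the time correlation within arm (or partial on monograph) and the logistic model with a monograph term.

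The cost is a few words, one covariate already in the data set and a slightly stricter criterion. With about 88% power at |r| = 0.2, a valid instrument would seldom be penalised.
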